2. STUDY OBJECTIVES, DURATION, AND STUDY SITES

2.1. Study Objectives

Objective 1: *Collect baseline data during the first 6 months before implementing any intervention component.*

Objective 2: *Implement the intervention in three phases: 1) provider education plus community outreach; 2) add provider assessment and feedback + patient reminder; and 3) add a CRC navigator program.*

Objective 3: *Create a grand model to test the overall effectiveness of the multilevel intervention on primary outcomes within and across levels, as well as separate models to assess effectiveness at each phase.*

Objective 4: *Identify potential interaction or mediation effects and assess such effects on primary outcomes.*

Exploratory Objective 5: *Implement a local innovation, IL ColonCARES Program, and assess its feasibility and effectiveness on the follow-up of abnormality.*

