3. STUDY DESIGN AND PROCEDURES

3.1 Study Design

We will use a stepped wedge cluster randomized trial design to assess the effectiveness of our proposed multilevel intervention. Although it will be preferable to use a traditional cluster-randomized trial to test our multicomponent, multilevel intervention, we will need a larger number of clusters, which will be more expensive and infeasible. Also, it is unacceptable for our partner(s) assigned to a control group to not benefit from well-studied evidence-based interventions. Since the stepped wedge design retains some elements of randomization and has the advantage for multiple data collection points over a long period and allows clusters to act as their own control, it is the best alternative to the gold standard.

In the UH3 Implementation phase, we will partner with four FQHCs. We will randomize the four FQHCs to either group 1 or group 2. The biostatistician will conduct the randomization independently from the research team. The difference between the two groups is that group 2 will start the implementation later. We will implement our multilevel intervention in three phases. In phase 1, we will implement the provider education and community outreach component. In phase 2, we will add the mobile patient reminder and the provider assessment and feedback components. In phase 3, we will add the CRC patient navigation component. Figure 1 shows our stepped wedge study design.

Figure 1: Stepped Wedge Study Design.

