ILColonCARES Program Many safety net settings with low resources offer FOBT/FIT as the initial screening option for their patients [42, 43]. However, providers in these settings often face an ethical dilemma: whether to offer no screening or to offer the screening knowing that the patient with a positive FOBT/FIT result cannot obtain timely follow-up colonoscopy services. In Chicago, the lack of specialty services for colonoscopy access within our safety net system is a significant problem with the average wait of 18 months to complete a diagnostic colonoscopy. This alone can significantly contribute to disparities in colorectal cancer mortality with studies showing that a one year delay in follow up for a positive FIT can result in a twofold increase in colorectal cancer risk [44]. Thus, it is important to increase the ability of safety net providers to access high quality and timely colonoscopies for their underinsured or uninsured patients when a follow-up is needed. ILColonCARES Program is a HIPAA compliant web-based portal designed and developed using a user experience approach to link non-networked healthcare systems. Some hospital health systems in Chicago have committed to providing no-cost colonoscopy services to uninsured FIT positive individuals. The ILColonCARES Program overcomes many barriers to receipt of colonoscopy services across systems: 1) access to care for uninsured patients, 2) point of service scheduling, 3) bidirectional communication. The ILColonCARES Portal was created by a CDC funded program and is housed in the University of Chicago. Our partner FQHCs will have access to the portal.

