3.5 Data Sources

During the first three months, we will work with the Quality Improvement Department at each partner site to collect baseline data on primary outcomes through the existing electronic medical record or chart reviews. After we start implementing the multilevel intervention, we will collect primary outcome data each quarter until the completion of the 4-year study period. Table 2 summarizes the primary outcome measures.

Table 2. Outcome Measures for the Multilevel Intervention

Outcome	Operational Definition	Data Sources	Data Collection Period	Level of Data Analysis
Patient CRC screening rates	Numerator: # of patients completed CRC screening Denominator: # of patients eligible for CRC screening	• EMR • Chart reviews as needed	Every quarter	Level 2, Level 3, Level 4
CRC ordering rates	Numerator: # of patients received order for CRC screening Denominator: # of patient eligible for CRC screening	• EMR • Chart reviews as needed	Every quarter	Level 2, Level 3, Level 4
Patient notification rates (FOBT/FIT +)	Numerator: # of patients notified Denominator: # of patients had FOBT/FIT +	• EMR • Chart review as needed	Every quarter	Level 2, Level 3, Level 4
Time to notification of positive results	# of days between notifying a patient with a positive result and the result available to the provider	• EMR • Chart reviews as needed	Every quarter	Level 2, Level 3, Level 4
Follow-up diagnostic evaluation referral rates	Numerator: # of patients received referral for evaluation Denominator: # of patients had FOBT/FIT +	• EMR • Chart reviews as needed	Every quarter	Level 2, Level 3, Level 4
Time to referral for follow-up diagnostic evaluation	# of days between the referral and the result available to the provider	• EMR • Chart reviews as needed	Every quarter	Level 2, Level 3, Level 4
Follow-up diagnostic evaluation completion rates	Numerator: # of patients completed diagnostic evaluation as ordered Denominator: # of diagnostic evaluation referral made	• EMR • Chart reviews as needed	Every quarter	Level 2, Level 3, Level 4
Time to completed diagnostic evaluation	# of days between the positive FOBT/FIT result available to the provider and the completion of the diagnostic evaluation	• EMR • Chart reviews as needed	Every quarter	Level 2, Level 3, Level 4

* Level 2 = Provider level; Level 3 = Clinic level; and Level 4 = organization level.

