4. DATA ANALYSES

In order to evaluate the effect of the multilevel, multicomponent intervention, we will take a step-by-step approach. First, each intervention effect at each time phase will be estimated separately using linear-mixed effects models. The estimate of intervention effect in each model will be used to test if additional intervention component significantly affects outcome measures. Next, we will develop a grand model including all three intervention effects simultaneously in addition to the models described above.

In this study, patients are nested within providers and providers are nested within clinics. The problem with nested data structures is that they violate the independence assumption of traditional regression models. Thus, we will use multilevel modeling to analyze our data. We will start with the unconditional three-level random intercept models:

$$\text{Level - 1: } Y_{ijk} = \beta_{0jk} + \epsilon_{ijk};$$

$$\text{Level - 2: } Y_{ijk} = \beta_{0k} + u_{jk} + \epsilon_{ijk}$$

$$\text{Level - 3: } Y_{ijk} = \beta_0 + v_k + u_{jk} + \epsilon_{ijk}$$

where Y_{ijk} is the observed outcome for patient i with provider j in clinic k . β_0 is the mean response across all clinic. v_k is the random effect of clinic k , u_{jk} is the random effect of provider j , and ϵ_{ijk} is the residual error. The random effects and residual errors are assumed independent of one another.

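### Time to completed diagnostic evaluation has no rule for FOBT/FIT-positive patients still waiting and no rule for assigning a patient to a phase, so mean days cannot measure the phase effect reliably

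*Combined protocol and SAP*

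**What the plan says.** Section 3.5 presents Table 2 as the primary outcome measures. One row is time to completed diagnostic evaluation, the number "of days between the positive FOBT/FIT result available to the provider and the completion of the diagnostic evaluation". The rows for time to notification and time to referral have the same structure. No row gives a value, a censoring date or an exclusion rule for a patient in whom the event has not happened.

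On the model, Section 4 says: "First, each intervention effect at each time phase will be estimated separately using linear-mixed effects models". It continues: "Next, we will develop a grand model including all three intervention effects simultaneously in addition to the models described above". The modelled quantity is the observed outcome of a patient, nested in provider and clinic. One binary outcome, adherence to diagnostic evaluation within 9 months of a positive result, gets a logit model.

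On the design, Section 3.1 says: "The difference between the two groups is that group 2 will start the implementation later". Navigation is the last component added. On waits, the ILColonCARES paragraph of Section 3.2.2 reports, for Chicago's safety net, "the average wait of 18 months to complete a diagnostic colonoscopy".

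Table 2 also has a completion rate with "Denominator: # of diagnostic evaluation referral made" and no time window.

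**The concern.** A patient still waiting at data extraction has no number of days. In a linear model of observed days that patient drops out, and the ones who drop out are disproportionately those with long waits. How many drop out depends on how much follow-up remains, which is tied to phase: patients first exposed to the later components have the least time left before October 2023.

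The result also depends on which date places a patient in a phase, and the plan does not say. If it is the result date, late phases contain only short completed waits. If it is the completion date, a late phase contains a backlog of long waits that began under earlier phases. At stake is whether a primary outcome can show a true shortening at its right size and sign, and whether the method is fixed before the data are seen.

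**Working it through.** The plan gives no sample size, effect size or delay figure for this outcome, so there is no figure of its own to reproduce. What follows is an illustration.

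**Inputs**
- Study length of 48 months (Section 2.2, November 2019 to October 2023).
- Baseline of 6 months (Section 2.1: "Collect baseline data during the first 6 months before implementing any intervention component"; Section 3.5 says three months).
- Step dates are assumed because Figure 1 is not shown: phases 1, 2 and 3 start at months 6, 18 and 30 in group 1 and at months 12, 24 and 36 in group 2.
- Mean wait m of 6 months (assumed) or 18 months (Section 3.2.2, citywide).
- Exponential waits, positives spread evenly over time, everyone eventually completing (all assumed). Gamma waits with shape 2 are the sensitivity case.

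**1. Share with no value at study end**

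Share = (m/48) × (1 − exp(−48/m)). This gives 12.5% for m = 6, 24.5% for m = 12 and 34.9% for m = 18.

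**2. No true effect, no calendar term**

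Simulated completers, least squares on days with group and phase terms. Phase 3 minus baseline, in months:

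| Phase assigned by | mean 6 | mean 18 | mean 18, gamma |
|---|---|---|---|
| Result date | -2.7 | -9.5 | -10.0 |
| Completion date, only positives after study start | +3.5 | +10.4 | +11.4 |
| Completion date, earlier positives included | 0.0 | -0.1 | 0.0 |

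The third row is zero apart from simulation error. Adding calendar-quarter terms brings every entry to within 0.2 of zero, provided waits are equal across FQHCs.

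**3. No true effect, unequal waits, calendar terms included**

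Mean waits of 12 months in group 1 and 18 in group 2 give these errors for phases 1 to 3:
- By result date: -0.84, -0.57, +0.62.
- By completion date with positives after start: +1.74, +2.76, +2.69.

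With the groups swapped they become about +0.85, +0.60, -0.53 and -1.7, -2.65, -2.65. The error can therefore reach about 0.9 and 2.8 months, in either direction.

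**4. True effect under the rule with no artefact**

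Suppose the completion rate doubles when phase 3 starts, so that the long-run mean falls from m to m/2. Among patients completing t months later, the mean wait is

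[m/2 + exp(−2t/m)(3m/2 + t)] / [1 + exp(−2t/m)].

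For m = 18 this is 18.0 at t = 0, 17.1 at 6 and 15.3 at 12, because the backlog completes in the same phase. Average it, weighted by completions, over 18 months of phase 3 in group 1 and 12 months in group 2:
- m = 18: 738.4/44.4 = 16.6 months, a change of -1.4 where the long-run change is -9. The simulated regression gives -1.3 (gamma -3.0).
- m = 6: 160.5/35.9 = 4.5 months, a change of -1.5 where the long-run change is -3. The regression gives -1.5.

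**5. Same setting with calendar-quarter terms**

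The phase 3 estimate becomes +2.3 (mean 18), +1.4 (gamma) and +0.8 (mean 6). The sign is wrong in all three; at an 18-month mean the exact size varies somewhat with simulation size. The reason is that once both groups are in phase 3, the group that started first has cleared more backlog. The model reads this as a lasting group difference, and the phase terms offset it.

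**6. Censored model on the same schedule**

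A discrete-time complementary log-log model on person-months, with quarter, months since result, group and time-varying phase, was run on 1,500,000 positives. It gives a phase 3 hazard ratio of 0.99 to 1.00 with no effect and 1.99 to 2.04 when the rate truly doubles. With a logit link the doubled rate is an odds ratio of 2.06: monthly completion 1 − exp(−1/18) = 5.4% against 1 − exp(−1/9) = 10.5%.

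**The case against.** The strongest reply is that quarterly extraction from an EMR that predates the study most naturally counts completions in the quarter in which they occur, whenever the positive result arose. Under that reading nothing spurious appears. This stands. A reader might infer that the plan will manufacture a shortening of about 9 months, but the documents do not support that. It needs assignment by result date, no calendar adjustment and an 18-month wait, and the plan states none of these for its analysis. Nor does any section say that only completers will be analysed; that follows only from taking the definition and the model as written.

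The 18-month figure is a Chicago safety-net average, given in a paragraph about underinsured and uninsured patients. From the partner table in Section 2.2, the uninsured share is (48,357 × 9.3% + 51,343 × 16.5% + 51,235 × 30.2% + 37,102 × 35.1%)/188,037, or about 22%. The 6-month results deserve at least equal weight.

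The equations in Section 4 are templates. They contain no phase term either, although phase effects are plainly planned. They do not show that calendar time is excluded, only that it is not mentioned.

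One might also read the 9-month outcome and Table 2 as contradictory. They are not. Section 4 calls the 9-month outcome patient-level, while Table 2 lists Levels 2 to 4. It already counts a patient still waiting at 9 months as non-adherent. Completion per referral is a legitimate process step. What is missing is a follow-up cutoff for the 9-month outcome.

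Finally, the dates would allow a censored reanalysis later. That is true, but the choice would then be made after the data are seen.

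**Conclusion.** The gap is real and should be closed; it does not undermine the trial as a whole. A primary outcome has a value only for completers, the plan names no method for those still waiting, and the phase assignment rule is unstated. Mean days did poorly under every assignment rule tried. By result date, or by completion date among positives after study start, it shows a phase difference where none exists unless calendar time is modelled, and some error remains if waits differ between the groups. By completion date with earlier positives, the difference is correctly zero under no effect, but a true halving is muted and calendar terms turn it the wrong way.

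Directions and sizes rest on the assumed step dates and wait distributions. No delay figures are given for notification or referral, so no size can be put on those two rows. The 9-month outcome is a minor wording point.

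**What to change.** In Table 2 and Section 4, define time to completion as time-to-event from the date the result is available, in all FOBT/FIT-positive patients, and treat time to notification and time to referral likewise.
- Censor at the last data extraction, or at recorded death or departure from the FQHC.
- Enter phase as time-varying, with months-since-result, calendar-quarter and FQHC terms and the planned provider and clinic random effects. A discrete-time logistic model on person-months keeps the logit form already in Section 4.
- State how the completion date is obtained when the evaluation is done elsewhere, since the portal is meant "to link non-networked healthcare systems". Chart review is already a listed source.

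Minor wording: restrict the 9-month outcome to positives with 9 months of possible follow-up (results available by 31 January 2023 if data close on 31 October 2023), assign phase by result date, and keep completion per referral as a process measure.

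Cost: the event dates are already needed for Table 2. Death and departure dates may be an added EMR item; where they are missing, a sensitivity analysis censoring at last contact is advisable. The summary is less simple than mean days. The large simulation shows low bias, not adequate precision, and with four FQHCs precision will be limited. The 9-month outcome loses the last 9 months of positives, and windows that span a phase change dilute its contrast.

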The multilevel intervention components will include 1) provider education, 2) provider assessment and feedback, 3) patient reminder using mobile platform, 4) patient navigation, and 5) community outreach. The first three components will be implemented as part of the quality improvement project at the partner FQHCs. During the first six months, we will collect baseline data at our partner FQHCs. After we start implementing the multilevel intervention, we will collect outcome data every three months until the completion of the 4-year study period. At the clinic and provider levels, we will work with the Quality Improvement Department to collect outcome data on 1) CRC screening rates, 2) CRC screening order rates, 3) CRC screening completion rates, 4) follow-up diagnostic evaluation rates, 5) follow-up diagnostic evaluation completion rates, and 5) time to completion of diagnostic evaluation. At the patient level, we will collect data on patient navigation service utilization and the satisfaction of the services.

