5. STUDY MANAGEMENT

5.1 Data Management

During data extraction from EMR, the medical record numbers will be converted to unique study numbers. Data files used for statistical analyses will have only unique study numbers and will not contain the 18 HIPAA personal health information identifiers. We will work with the University of Chicago Center for Research Informatics' bioinformatics and clinical trial management core to manage our data, and all data will be entered into RedCAP (Research Electronic Data Capture) at the University of Chicago. REDCap is a clinical data warehouse. The data storages at REDCap are secure, encrypted, and compliant with HIPAA.

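### Table 2 sets all eight primary outcomes at provider, clinic and organisation level, while Section 4 models individual patients without an organisation term; no primary level or weighting is named

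*Combined protocol and SAP*

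**What the plan says.** Section 3.5 states that "Table 2 summarizes the primary outcome measures". The table has eight rows. Five are proportions: screening, ordering, notification, referral and completion of diagnostic evaluation. Three are times; time to referral, for example, is the number "of days between the referral and the result available to the provider". Every row carries the same three analysis levels, explained in the footnote: "Level 2 = Provider level; Level 3 = Clinic level; and Level 4 = organization level". Level 1, the patient, is not listed.

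The protocol summary (Study Intervention and Measures) agrees with the table: "At the clinic and provider levels, we will work with the Quality Improvement Department to collect outcome data on" the screening and follow-up measures. Its patient-level data are confined to use of navigation and satisfaction with it.

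Section 4 takes a different unit. It says that "In this study, patients are nested within providers and providers are nested within clinics", and its response Y "is the observed outcome for patient i with provider j in clinic k". The levels stop at the clinic. For the intervention effects, "each intervention effect at each time phase will be estimated separately using linear-mixed effects models", followed by a grand model with all three effects. One patient-level outcome is called dichotomous and given a logit model: follow-up of a positive result within 9 months, a window that no row of Table 2 contains. Section 3.1 randomises the four FQHCs, which are Table 2's Level 4, to two groups.

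Section 5.1 says that at extraction "the medical record numbers will be converted to unique study numbers", which implies that individual records will be available.

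**The concern.** The two sections describe different data sets for the same outcomes, and no text connects them. If Y is a patient record, all five proportions are binary. Calling only one outcome dichotomous therefore suggests that the five would enter the linear mixed model as quarterly rates, as Table 2 and the summary imply.

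With rates as Y and no weights stated, a provider with few eligible patients counts as much as one with many. Each FQHC's influence also changes with the level chosen. If the programme works better in some FQHCs than in others, the provider, clinic, organisation and patient analyses estimate different averages. The plan names none of them as primary and does not say whether it wants the average effect over patients or over clusters. The choice could then be made after the results are known. Separately, the randomised unit has no term in the written model.

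**Working it through.** **Inputs.** The FQHC characteristics table in Section 2.2, in its row order (FQHC 1 to 4):
- patients: 48,357; 51,343; 51,235; 37,102
- providers: 60; 21; 35; 20
- clinics: 11; 12; 5; 7
- baseline screening rates: 30.0%, 32.9%, 35.0%, 31.0%

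**The plan's own totals.** 48,357 + 51,343 + 51,235 + 37,102 = 188,037 patients and 11 + 12 + 5 + 7 = 35 clinics. Both match Section 1.2. Providers sum to 136. The plan gives no sample size, power or effect size to check against.

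**Unequal denominators.** Section 2.2 puts at least 10% of patients at age 50 or over. Applying that floor to every FQHC (an assumption), patients aged 50 or over per provider = 0.10 × patients / providers:
- FQHC 1: 4,835.7 / 60 = 81
- FQHC 2: 5,134.3 / 21 = 244
- FQHC 3: 5,123.5 / 35 = 146
- FQHC 4: 3,710.2 / 20 = 186

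The sampling variance of a rate is p(1 − p)/n. At the same p, a typical provider rate in FQHC 1 has about 244/81 = 3.0 times the variance of one in FQHC 2, yet both count once in an unweighted linear model.

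**Weight of each FQHC by level.** Weight = the FQHC's share of the units at that level.

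| Level | FQHC 1 | FQHC 2 | FQHC 3 | FQHC 4 | Pooled baseline rate |
|---|---|---|---|---|---|
| Patient | 25.7% | 27.3% | 27.2% | 19.7% | 32.35% |
| Provider | 44.1% | 15.4% | 25.7% | 14.7% | 31.88% |
| Clinic | 31.4% | 34.3% | 14.3% | 20.0% | 31.91% |
| Organisation | 25.0% | 25.0% | 25.0% | 25.0% | 32.22% |
| Largest / smallest | 1.76 | 2.22 | 1.91 | 1.70 | |

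**Provider count of FQHC 1.** The summary and Section 2.2 give 20 to 35 providers per cluster, but the table gives 60 for FQHC 1. Capped at 35, the total is 111 and the provider shares are 35/111 = 31.5%, 21/111 = 18.9%, 35/111 = 31.5% and 20/111 = 18.0%. The largest-to-smallest ratios become 1.26, 1.81, 2.21 and 1.39.

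**Consequence for the effect.** Summary at a level = sum of weight × FQHC effect. The effects below are assumed, in percentage points.

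| Effects in FQHC 1/2/3/4 | Patient | Provider | Clinic | Organisation |
|---|---|---|---|---|
| 10/10/10/10 | 10.0 | 10.0 | 10.0 | 10.0 |
| 15/5/5/5 | 7.6 | 9.4 | 8.1 | 7.5 |
| 5/15/5/5 | 7.7 | 6.5 | 8.4 | 7.5 |

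For effects spread over at most 10 points, the largest gap between two levels is 10 × half the sum of the absolute weight differences. The worst pair is provider against clinic: 10 × ½ × (0.127 + 0.188 + 0.114 + 0.053) = 2.4 points. With FQHC 1 capped at 35 providers, the same pair gives 10 × ½ × (0.001 + 0.154 + 0.172 + 0.020) = 1.7 points.

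**Weights in a patient-level mixed model.** Such a model does not weight simply by patient numbers. For the overall mean, FQHC weight is proportional to clinics / [v_c + v_p/J + (1 − v_c − v_p)/(mJ)], where J = providers per clinic, m = eligible patients per provider (10% assumed), and v_c and v_p = clinic and provider variance shares. For FQHC 1 this gives 25.7% at v_c/v_p = 0/0, 32.3% at 0.10/0.02, 34.8% at 0.05/0.05, 35.8% at 0.01/0.02 and 39.5% at 0.02/0.10. The variance shares are assumed.

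**The case against.** The best defence is that Table 2 lists the grouping levels of one multilevel model, with the patient as an unstated Level 1. Its numbering of provider as 2 and clinic as 3 matches Section 4, Section 5.1 implies record-level extraction, and Objective 3 assigns overall effectiveness to a grand model. This reading is possible. However, no text states it, the summary points the other way, and Section 4 has no Level 4. The grand model combines the three phase effects; it does not settle whether Y is a record or a rate.

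Several stronger readings are tempting, and the documents do not support them.
- *Every primary outcome is a rate.* Three of the eight are times in days, so a binomial model alone is not a complete remedy.
- *The levels must give conflicting answers.* Under a common effect they have the same expectation. The pooled baseline rates differ by only 32.35 − 31.88 = 0.5 point.
- *Quarters in which a provider has no positive FOBT/FIT lose data.* Such a cell contains no patient for those outcomes, so omitting it loses no observation. The difficulty with tiny denominators is noise and weighting. The documents give no testing or positivity figures from which to count empty cells.
- *FQHC 1 would dominate with 44.1% of the weight.* That depends on the count of 60 providers, which conflicts with the stated 20 to 35. Simple shares are also not the weights of the planned estimator: a mixed model lies between them, and in a stepped wedge the weights also depend on crossover timing.

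**Conclusion.** The inconsistency stands. Table 2 and the summary place the primary outcomes at aggregate levels, and Section 4 analyses patients with no term for the randomised organisation. The plan names neither a primary level nor a weighting.

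The numerical consequence is conditional and moderate. If Table 2 is followed with unweighted rates, FQHC weights shift 1.7- to 2.2-fold between levels (1.3- to 2.2-fold with the provider cap). The estimates then diverge only if effects differ between FQHCs. For a 10-point spread the gap is at most about 2.4 points, or 1.7 with the cap. These bounds use simple unit shares, with total patients standing in for eligible patients, whose number per FQHC is not given. The documents give no information on how far effects vary. Under a common effect the expected answers agree and only precision differs. The point deserves correction before analysis; it does not show that the planned estimate is biased.

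**What to change.** In Table 2 and Section 4, name one primary inferential analysis per outcome, based on patient-level records with provider and clinic as grouping levels and the FQHC included in the model. State whether the FQHC term is fixed or random, since four units are few for estimating a variance.

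- For the five proportions, use a logit or binomial model. Where only counts exist, model numerator and denominator, never an unweighted rate.
- For the three time outcomes, analyse patient-level days.
- State whether the target is the patient-average or the cluster-average effect, because a patient-level mixed model does not settle this by itself.
- Align the protocol summary with the record-level extraction implied by Section 5.1.
- Label any provider-, clinic- or organisation-level analyses as secondary. They remain useful, since some components act at those levels.
- Reconcile the 60 providers listed for FQHC 1 with the 20 to 35 per cluster.

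The cost is mainly wording in Table 2, Section 4 and the summary, plus somewhat more analysis work. Record-level extraction already appears to be planned.
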